### **4.0 Enrollment/Randomization**

All cystectomy cases scheduled by the urologists at IU Health University Hospital will be identified. Subjects will be contacted face-to-face prior to surgery by one of the research team members. They will be informed about the study and all questions will be answered. The potential subjects will be given a copy of the informed consent form and authorization form. The subjects will then be contacted face-to-face in POCU on the day of surgery and if participation is agreed, written consent will be taken. All patients will undergo a standardized enhanced recovery perioperative care pathway designed and agreed upon by the perioperative team of anesthesiologists and surgeons.

A total of 160 subjects will be randomized by a computer program into four groups (40 in each group):

1. Thoracic epidural– epidural bupivacaine 0.05%/hydromorphone 0.05mg/ml mix will be given throughout the duration of their epidural analgesia.
2. Rectus Sheath Block - 20 mL of liposomal bupivacaine diluted with 40 mL of 0.125% bupivacaine and 40 ml of injectable saline for a total of 100 mL. The 100 mL will be injected into 4 locations below the rectus abdominis muscle.
3. Surgeon infiltration with Liposomal Bupivacaine (LB) – 20 mL of liposomal bupivacaine diluted with 40 mL of 0.125% bupivacaine and 40 ml of injectable saline for a total of 100 mL. The 100 mL will be injected throughout the incision site by the surgeon at the end of surgery, prior to abdominal wall closure.
4. Surgeon infiltration with Standard Bupivacaine (SB) – 60ml of 0.5% bupivacaine will be diluted with 40ml of saline for a total of 100ml. The 100 mL will be injected throughout the incision site by the surgeon at the end of surgery.

Randomization will be performed using Research Randomizer. The primary investigator will inform the person doing the block as to what group the patients are randomized to

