**[name]**  
**Medical Student, Indiana University School of Medicine**

**Version 5.0 10-21-19**

## 1.0 Background

Indiana University Hospital is a large academic health center that performs a large number (~180) of cystectomies per year. Cystectomy is a urologic procedure that involves the radical removal of the bladder, with subsequent need for urinary tract reconstruction. The reconstruction requires harvesting of portions of the small and/or large bowel, and can be in the form of an ileal conduit, orthotopic bladder replacement, or continent urinary reservoir such as an "Indiana Pouch". The postoperative course usually spans on average a 7-day inpatient hospital stay, with the majority of the issues surrounding management of postoperative pain and subsequent ileus. Currently, there is no standard of pain control in cystectomy, though adjunctive mechanisms of analgesia are often utilized to decrease opioid usage. Opioid use has long been associated with postoperative ileus, nausea and vomiting, aspiration, prolonged hospital stay, and several other side effects. Postoperative pain may also decrease patient satisfaction while increasing length of hospital stay and hospital costs. Without a standard practice for postoperative pain control in cystectomy, our study aims to compare thoracic epidural versus rectus sheath block versus surgeon infiltration of local anesthesia for cystectomy. With studies indicating improvements in perioperative outcomes for all three techniques, we believe we should compare these three methods for possible incorporation of the best technique for our enhanced recovery after surgery (ERAS) protocol for cystectomy. This will be done by collection of post-operative pain scores (VAS) at both resting and with movement. The VAS (Visual Analog Scale) pain scores will be measured at 24, 48, 72 and 96 hours under an advanced recovery perioperative care pathway.

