### **3.0 Inclusion/Exclusion**

Inclusion criteria:

- Patients undergoing cystectomy surgery
- ASA class 1, 2, 3 or 4
- Age 18 or older, male or female
- Desires Regional anesthesia for postoperative pain control

Exclusion criteria:

- Any contraindication for thoracic epidural, such as coagulopathic states or pre-existing hardware in the thoracic epidural space.
- History of substance abuse in the past 6 months.
- Patients on more than 30mg morphine equivalents of opioids daily.
- Any physical, mental or medical conditions which in the opinion of the investigators, may confound quantifying postoperative pain resulting from surgery.
- Known allergy or other contraindications to the study medications (Acetaminophen, Gabapentin, Bupivacaine, Hydromorphone).
- Postoperative intubation.
- Any patient with history of neuropathic bowel or bladder dysfunction

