## **7.0 Statistical consideration**

Primary outcome: VAS score with movement at 48 and 72 hours

Primary Research Hypothesis: Thoracic epidural will provide lower postoperative pain scores compared to each of the other three methods used for cystectomy as measured by VAS scores at 24, 48, 72, and 96 hours under an enhanced recovery perioperative care pathway.

Secondary outcomes: Narcotic usage after 1, 24, 48, 72, and 96 hours. Pain scores using VAS at rest and on knee flexion at 1, 24, 48, 72, and 96 hours. Nausea scores at 1, 24, 48, 72, and 96 hours. Sedation scores at 1, 24, 48, 72, and 96 hours. Time to first flatus, postoperative creatinine, hospital length of stay (hospital length of stay (LOS) will be collected via EMR of the admission and discharge date to calculate the LOS), ileus, hypotension (defined as BP decrease of more than 20%), and ambulation/anytime out of bed (up in chair, to bathroom and walking in hall with PT/nurse) activity will also be recorded daily. It will be recorded as yes/no.

If the patient is discharged within 96 hours, every effort will be made to obtain data points, but we will not consider these data point deviations since our 96-hour data point will not change the integrity of the study.

Secondary Research Hypotheses: Thoracic epidural will show improved patient satisfaction scores and decreased nausea and sedation scores compared to each of the other three treatments.

Statistical analysis will be performed using a standard statistical program (SAS or SPSS). All data will be summarized (means, standard deviations, standard errors, and ranges for continuous variables; frequencies and percentages for categorical variables) by group. Demographic data will be compared between the four groups using ANOVA or chi-square tests as appropriate. The primary outcome, VAS ( Visual Analog Scale) at 48 and 72 hours, will be compared between the

groups using repeated measures ANOVA; the model will include fixed effects for group, time, and the group by time interaction and random effects to allow correlations between the two times and different variances for the two times.

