Pain and satisfaction scores and opioid usage over time will be analyzed using repeated measures ANOVA. Nausea and sedation scores will be compared between groups at each time point using Mantel-Haenszel chi-square tests for ordered categorical data. Time to first flatus, postoperative creatinine, and LOS will be compared between the groups using one-way ANOVA. The binary outcomes of incidence of ileus, hypotension (defined as BP decrease of more than 20%), and incidence of respiratory depression will be analyzed using logistic regression. Distributions of the continuous variables will be examined, and a transformation of the data (e.g. natural logarithm) or nonparametric tests will be used as necessary. A 5% significance level will be used for all comparisons.

Based on prior studies, the coefficient of variation for the VAS ( Visual Analog Scale) score at 48 and 72 hours is estimated to be 0.70. With a sample size of 40 per group the study will have 80% power to detect a ratio of means of 1.5 for VAS score between any two of the four treatment groups, assuming two-sided tests each conducted at a 5% significance level.

All patients will receive a phone survey approximately 6 months after surgery to assess for pain, quality of life, and satisfaction of hospital stay. Quality of life is measured by how their pain interferes with their general activity, mood, walking ability, normal work, relations with other people, sleep and enjoyment of life. If after four attempts to contact the patient are unsuccessful, the survey will not be completed; this will not be considered a deviation as the survey is not critical to the overall data collection.

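### Diversion type is neither a listed data item nor a model term; recording planned diversion and adjusting for it would cheaply sharpen the bowel-recovery and LOS comparisons

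*Combined protocol and SAP*

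**What the plan says.** **Surgery.** Section 1.0: "The reconstruction requires harvesting of portions of the small and/or large bowel, and can be in the form of an ileal conduit", with orthotopic bladder replacement and a continent reservoir as the other forms. The same section names pain and ileus as the main problems of the postoperative stay, and gives one average stay of 7 days for cystectomy as a whole.

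**Eligibility.** Section 3.0 asks for "Patients undergoing cystectomy surgery" and sets no limit by type of diversion.

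**Allocation.** Section 4.0: "A total of 160 subjects will be randomized by a computer program into four groups (40 in each group"; "Randomization will be performed using Research Randomizer". No stratum, block or minimisation factor is described.

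**Data items.** The lists in sections 2.0, 4.0 (Study procedures) and 7.0 do not include diversion type, which is not mentioned after section 1.0. For baseline, section 7.0 says only: "Demographic data will be compared between the four groups using ANOVA or chi-square tests as appropriate".

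**Analysis.** Section 7.0: "Time to first flatus, postoperative creatinine, and LOS will be compared between the groups using one-way ANOVA". Ileus falls in the group of binary outcomes, of which the text says "incidence of respiratory depression will be analyzed using logistic regression", with no covariate named. For the primary VAS analysis, "the model will include fixed effects for group, time, and the group by time interaction".

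**The concern.** Reconstruction is the part of the operation carried out on the bowel, and by the protocol's own account it varies between patients. Flatus, ileus and LOS could plausibly vary with it. A factor of this kind, if planned before surgery, is a natural baseline covariate.

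As the plan stands, an imbalance in diversion between arms would not show in the planned tables. Any outcome variance due to diversion would stay in the residual of the planned tests. Ileus and LOS belong to two of the four aims in section 2.0, and the trial is meant to help choose a technique for the enhanced-recovery pathway, so these comparisons will be read closely.

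**Working it through.** **1. The plan's own figure.** The only stated calculation is for VAS (section 7.0): coefficient of variation 0.70, ratio of means 1.5, two-sided 5%, 40 per group, 80% power.

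- Log-scale SD = √ln(1 + 0.70²) = 0.6315; difference = ln 1.5 = 0.4055.
- n = 2 × (1.960 + 0.842)² × 0.6315² / 0.4055² = 38.1, so 39 per group.
- Power at 40 per group is 0.819 (normal) or 0.809 (noncentral t).

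The stated figure reproduces. Diversion does not enter it, and adjusting the secondary outcomes does not change it or the total of 160.

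**2. Assumptions.** The documents give no diversion mix, no diversion effect and no SD for LOS. Assumed: continent share p = 0.30 (range 0.20–0.40), effect d on LOS of 1–3 days, total SD of LOS 3–4 days. The group size of 40 is from section 4.0.

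**3. How often is there a 15-point imbalance?** Fifteen points is 6 of 40 patients. The SD of the difference in counts between two arms is √(2 × 40 × 0.30 × 0.70) = 4.10. With continuity correction, 5.5 / 4.10 = 1.34, a two-sided probability of 18%. Permuting 160 patients into four arms of 40 also gives 18%. The probability is about 12% at p = 0.20 and 21% at p = 0.40. For epidural against at least one of its three comparators, it is about 40% at p = 0.30.

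**4. What does that imbalance do?** The shift in the LOS difference is 0.15 × d: 0.15, 0.30 or 0.45 day for d = 1, 2 or 3. The standard error (SE) of a pairwise difference is SD × √(2/40): 0.67 day at SD 3 and 0.89 day at SD 4. At d = 2 the shift is 0.30/0.89 = 0.34 to 0.30/0.67 = 0.45 of an SE. Over all the assumed values it runs from 0.15/0.89 = 0.17 to 0.45/0.67 = 0.67.

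**5. What does adjustment gain?** The variance share explained is R² = p(1 − p)d²/SD², and the SE falls by 1 − √(1 − R²), with p = 0.30:

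| d (days) | SD (days) | R² | SE reduction |
|---|---|---|---|
| 1 | 4 | 0.013 | 0.7% |
| 1 | 3 | 0.023 | 1.2% |
| 2 | 4 | 0.053 | 2.7% |
| 2 | 3 | 0.093 | 4.8% |
| 3 | 4 | 0.118 | 6.1% |
| 3 | 3 | 0.210 | 11.1% |

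For outcomes with no assumed unit, such as flatus, the effect can be set at g = 0.25–1.0 within-type SD, with p from 0.2 to 0.5. Then R² = p(1 − p)g² / (1 + p(1 − p)g²), and the SE falls by 0.5% to 10.6%. That is worth 40.4 to 50 unadjusted patients per arm in place of 40.

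**6. Is the unadjusted test valid?** In simulation (100,000 two-arm comparisons, p = 0.30, no treatment effect), the rejection rate at 5% was 0.049 for g = 0.5 and for g = 1.0. Type I error is nominal.

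**The case against.** The strongest reply is that simple randomisation is sound. Chance imbalance is already allowed for in the ANOVA standard error, so leaving out a covariate is a loss of efficiency and not an error. That stands. The gain is also small under most of the assumed values, and every input that sets its size is assumed. That stands too.

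A reader might infer more than the documents support:

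- **That the arms are confounded by diversion.** Randomisation excludes this on average, and step 6 shows no inflation of type I error.
- **That an imbalance could never be examined.** Sections 8.0 and 9.0 keep identifiers until three years after completion, section 4.0 has all scheduled cystectomies identified, and LOS is taken from the electronic record. Linkage back to the surgical schedule should remain possible. What is missing is prespecification.
- **That the protocol assigns a bowel segment to each diversion, or says outcomes differ by diversion.** Apart from the name ileal conduit, section 1.0 does neither. A diversion effect is plausible but not documented.
- **That the primary VAS analysis, nausea, sedation or opioid use is affected.** The documents give no basis for a diversion effect on these.

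Stratifying with blocks also carries some risk of predictable allocation in a trial where the principal investigator tells the person performing the block which arm applies. It is fair to say that stratification is not required.

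The remaining point is that a covariate-adjusted model with a factor fixed in advance is a better choice than an unadjusted one-way comparison, at almost no cost.

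**Conclusion.** The point holds as a cheap improvement to secondary analyses. Diversion type is not listed for collection and is in none of the planned models, so the comparisons of flatus, creatinine, LOS and ileus are exposed to chance imbalance and give up some precision. Randomisation, type I error and the stated VAS power are not in question.

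Under the assumptions in step 2, adjustment shortens the SE of a pairwise LOS difference by about 1–11%, and by 3–5% for a 2-day effect. The shift from a 15-point imbalance is under half an SE at 2 days, so it would seldom reverse a conclusion by itself. If diversion has no effect on these outcomes, the gain is nil and the loss from adjusting is negligible.

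**What to change.** 1. Add planned diversion to the data collected before allocation, and record the diversion performed. The covariate should be the planned form: the performed one is known only after allocation and serves for description. The documents do not say when diversion is settled, so this should be stated.
2. Tabulate planned and performed diversion by arm alongside the demographic data.
3. In section 7.0, replace the one-way ANOVA for time to first flatus, LOS and creatinine with a linear model containing group and planned diversion, on a transformed scale where the planned distribution check calls for it. Add the same covariate to the logistic model for ileus. Fix the grouping of diversion types before the data are analysed.
4. For patients already randomised, take planned diversion from the pre-operative schedule.

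The cost is one or two data fields and slightly more analysis work, with the total staying at 160. Stratifying the remaining allocation by planned diversion is optional and not needed for most of the gain. If it is done, block sizes should be random and undisclosed.

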#### **Study procedures:**

Thoracic epidural placement will occur in the preoperative period. Both the rectus sheath block and the surgeon infiltration will occur at the end of the case. All procedures will be done using sterile technique with masks, hats, and sterile gloves. Thoracic epidurals and rectus sheath block will be placed under the supervision of the attending anesthesiologist on the acute pain service. Surgeon infiltration will be performed by the surgeon.

Patients will be randomized to one of the four arms by the research randomizer. On the day of surgery, the Principal Investigator will inform the person doing the block as to what group the patients are randomized to.

Thoracic epidural will be performed around T9-T10 interspace since that correlates with surgical incision dermatomes. Utilizing the loss-of-resistance technique, an 18-gauge needle will be inserted in the midline between the lumbar spinous processes and advanced until loss-of-resistance is felt. A small amount of preservative-free saline will be injected to ensure the location in the epidural space. After careful aspiration, a test dose of 2-3 mL local anesthetic containing diluted epinephrine will be injected and the heart rate will be monitored in case of accidental placement in an epidural vein.

---

Rectus sheath block will be performed at 4 locations below the rectus abdominis muscle, using an ultrasound. The locations will be both left and right abdomen, above and below the umbilical region.

Surgical wound infiltration will be performed by the surgeon at the end of the case. It will be performed via a direct technique. In the direct technique, anesthetic is injected after careful aspiration in small boluses into the subfascial tissues until the wound is adequately anesthetized.

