## **8.0 Privacy**

All study papers containing patient identifiers will be kept in each subjects' confidential study file accessible to only the research team. All records will be kept in a locked room in a locked cabinet that only authorized staff enters. Collected data from each enrolled participant will be recorded on Redcap, which is a secure web-based data collection tool. Three years after completion of the study, all electronic information and paperwork containing patient identifiers will be deleted or shredded.

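### The study lead relays each assignment on the day of consent, and the protocol describes no safeguard that conceals allocation from those who recruit or judge eligibility

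*Combined protocol and SAP*

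**What the plan says.** Four statements in section 4.0 and its Study procedures text describe how a patient reaches an arm.

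- **First contact:** "Subjects will be contacted face-to-face prior to surgery by one of the research team members".
- **Consent:** "The subjects will then be contacted face-to-face in POCU on the day of surgery and if participation is agreed, written consent will be taken". The person who takes consent is not named.
- **Draw:** "A total of 160 subjects will be randomized by a computer program into four groups (40 in each group"), and "Randomization will be performed using Research Randomizer".
- **Hand-over:** "The primary investigator will inform the person doing the block as to what group the patients are randomized to". The Study procedures text repeats this and adds the day: "On the day of surgery, the Principal Investigator will inform the person doing the block as to what group the patients are randomized to".

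Two other points bear on timing and discretion. The epidural arm has to be known before the operation, because "Thoracic epidural placement will occur in the preoperative period". Section 3.0 also lets investigators exclude a patient for any condition that they judge could confound the measurement of postoperative pain.

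**The concern.** Randomisation protects a comparison only if nobody who decides whether a patient enters can know, or reliably guess, the next assignment. Here the study lead knows each assignment and passes it on. Members of the research team approach patients, and one eligibility criterion is a matter of opinion. Consent and hand-over fall on the same day with no stated order.

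If an assignment were known before entry was settled, a patient could be approached, deferred or excluded because of it. The arms would then differ in prognosis before any treatment. Two features add to the worry: the protocol states in advance that it expects the epidural to be superior, and the procedures look different, so past assignments will be apparent to staff.

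**Working it through.** **1. Sequence of events.** The stated steps are first contact before surgery, consent in the preoperative area on the day of surgery, the principal investigator telling the operator the group on that same day, and epidural placement before the operation. Consent, the final eligibility judgement and release of the assignment therefore share one short window. The text does not give their order.

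**2. Search for a safeguard.** Four things would protect allocation:

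- *Independent custodian of the list:* none named. The only person the text describes as having the assignments is the principal investigator.
- *Release only after logged consent and eligibility:* not stated.
- *A physical or electronic barrier (envelopes, central release, locked module):* none. REDCap appears in section 8.0, but only for data capture: "Collected data from each enrolled participant will be recorded on Redcap".
- *Unpredictable order:* the tool is named, but blocking and strata are not described.

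Staff could follow sections 3.0 and 4.0 exactly, with an open list in the study lead's hands, and commit no deviation.

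**3. Could the analysis repair it?** The primary model in section 7.0 has group, time and their interaction as fixed effects, with random effects for the two times. It contains no prognostic covariates, and covariates could not remove selection on unmeasured prognosis in any case.

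**4. The plan's own figure.** Section 7.0 gives a coefficient of variation of 0.70, a ratio of means of 1.5, 40 per group and a two-sided 5% level.

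- Log-scale SD = √ln(1 + 0.70²) = 0.6315.
- Log-scale difference = ln 1.5 = 0.4055.
- Two-sample t-test power at 40 per group = 80.9%, so the stated 80% reproduces.

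The concern does not depend on this figure, but the same inputs set the scale for the illustration.

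**5. Illustration: what a selection shift would do.** Assume a mean VAS of 3, which is not in the documents. The SD is then 0.70 × 3 = 2.1. The standard error of a difference between two arms is 2.1 × √(2/40) = 0.470. With no true treatment difference:

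- Shift of 0.3 points in one arm: 0.3/0.470 = 0.64 standard errors, and the two-sided 5% test rejects 9.8% of the time.
- Shift of 0.5 points: 0.5/0.470 = 1.06 standard errors, and the test rejects 18.7% of the time.

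If the assumed mean runs from 2 to 5 with the same coefficient of variation, the ranges are about 7% to 16% for 0.3 points and 10% to 36% for 0.5 points. The log-scale version agrees: a spurious ratio of means of 1.10 gives about 10%, and 1.20 about 25%. The inflation applies to tests that involve the shifted arm, which are three of the six pairs.

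**6. Illustration: guessing.** Suppose one unblocked list of 4 × 40 were used and past assignments were known. Always guessing the group with most places left would be right about 31% of the time overall and about 54% over the last 10 patients (1,500 simulated lists), against 25% by chance. The single unblocked list is an assumption.

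**The case against.** The strongest reply is that this is silence, not a described fault. Somebody has to tell the operator which procedure to perform, and doing so on the day of surgery is fully compatible with concealment until consent. Section 4.0 also mentions written consent before it mentions randomisation, which fits assignment after consent. That stands: the hand-over sentence is not itself the defect. What is missing is a custodian and a release rule, and the order of paragraphs does not supply either.

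A reader might infer several stronger things that the documents do not support:

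- *That assignments are seen before consent.* No section says so.
- *That the principal investigator recruits, takes consent, or passes on assignments by word of mouth.* The text says only that a research team member makes contact and that the principal investigator informs the operator.
- *That many patients could be selected out.* About 180 cystectomies a year over 24 months is about 360, and 160/360 = 44%, so about 200 would not be enrolled. That number includes ineligible patients, those who do not want regional anesthesia and those who refuse. No eligibility or refusal rate is given, so the number open to discretion is unknown.
- *That every comparison is biased.* Bias needs foreknowledge that is both available and used, and a shift in one arm leaves the pairs without that arm untouched.

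The protocol also has an independent group monitor recruitment at least annually. That is useful oversight, but it does not hide the next assignment from anyone.

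**Conclusion.** The concern holds in a limited form. The written procedure has the study lead know and relay assignments on the day of consent, and it puts no barrier between the assignments and those who approach patients or apply the opinion-based exclusion. This is more than a missing detail, because the protocol can be followed to the letter with allocation unconcealed. Selective enrolment therefore cannot be ruled out from the documents; equally, they do not show that it occurs.

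The size of any bias is unknown. The error rates of about 10% and 19% rest on an assumed mean VAS of 3 and on assumed shifts of 0.3 and 0.5 points. They show sensitivity and do not predict bias. The change should be made, and the sample size is not affected.

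**What to change.** Add a short allocation paragraph to section 4.0:

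- Someone already on the project who does not recruit, judge eligibility or score outcomes (for example the statistician) prepares and holds the computer-generated list.
- The list uses permuted blocks of varying size. The sizes are not disclosed to recruiters, since past assignments will be apparent and fixed blocks would let the last places in each be worked out.
- The list is loaded into a locked REDCap randomisation module or, failing that, sequentially numbered opaque sealed envelopes.
- Each assignment is released one patient at a time, only after signed consent and eligibility are logged with a time, and the person doing the block is then told.

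One criterion in section 3.0, postoperative intubation, cannot be judged by that point. The paragraph should say that the log covers the criteria that can be assessed before surgery, and how the remaining one is handled in the analysis.

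Section 9.0 gives an August 2019 start and this version is dated October 2019. If enrolment has begun, record how assignments so far were held and released, and apply the new procedure to the rest.

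The cost is a few hours of set-up and a few sentences of protocol text. It needs no extra staff provided that such a person exists on the project, which the documents do not show.
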